1.0 Objectives

1.1 Study Objectives

Often comorbid with obesity, nonalcoholic fatty liver disease (NAFLD) is the leading cause of chronic liver disease in the United States affecting 75-100 million adults, of which 15-20 million have the more severe variant nonalcoholic steatohepatitis (NASH).(1-3) Conservative estimates project a doubling in NASH by 2025.(4-6) The most advanced forms of NAFLD are associated with increased liver-related mortality and lower overall survival. The most effective treatment for NAFLD remains adopting healthy dietary and exercise patterns,(7-14) however NAFLD patients are among the least physically active individuals.(15) Predicting exercise behavior on an individual level is highly complex due to differing motivation, physiologic response to and subjective experience of exercise as well as emerging genetic evidence.(16, 17) The human genome and regulation of gene expression is influenced by physical activity. Patatin like phospholipase-3 (PNPLA3) rs738409 polymorphism (GG, GC and CC genotypes) plays a crucial role in the development of NAFLD.(18-24) The GG genotype is both associated with advanced NAFLD,(18, 25-27) and predicts response to physical activity.(10, 28) Patients with NASH have extensive extrahepatic disease(29) and are hypercoagulable.(30-42) NASH is a prothrombotic state with fibrinolytic dysfunction through elevated plasminogen activator inhibitor (PAI-1), an independent risk factor for venous thromboembolism (VTE). Consequently, patients with NASH are predisposed to VTE;(30-32) the risk of portal vein thrombosis (PVT) in NASH is 210% greater than in other liver disease.(30, 31) NASH patients are also at increased risk for pulmonary embolism (PE) and deep vein thrombosis (DVT). The most advanced forms of NASH have the greatest thrombotic risk. While studies observe that change in diet, weight and physical activity patterns improve NASH, it is not clear whether these lifestyle changes also reduce the elevated clot risk, however, moderate-intensity exercise leads to improved fibrinolysis in healthy persons.

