1.3 Secondary Study Endpoints

Secondary Outcomes are as follows: (1) Change in PAI-1 after 16-week exercise regimen; (2) Change in other markers of hemostasis [von Willebrand Factor (vWF), P-selection, Protein S, Protein C, Factor VII, Factor VIII, Fibrinogen, Antithrombin,] after 16-week exercise regimen; (3) Change in PAI-1 stratified by PNPLA3 genotype after 16-week exercise regimen; (4) Correlation between loss of hepatic fat as measured by magnetic resonance imaging proton density fat fractionation (MRI-PDFF) and changes in hemostatic markers after 16-week exercise regimen; (5) Correlation between maximal oxygen consumption (VO₂ max) and hemostatic markers after 16-weeks of exercise; (6) health-related quality of life (HRQOL) change following exercise intervention

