8.3 Statistical methods
Subjects will be compared across multiple important baseline demographic, laboratory, imaging and histologic data. Results will be expressed as means with standard deviations. Chi-squared and Fisher's exact test will be used to analyze our categorical endpoints. Student's t test and Mann-Whitney Rank Sum test will be used for secondary analysis of differences in numerical lab data. Paired t-tests will be used where appropriate (e.g. comparison of pre- and post-intervention fibrosis parameters such as NFS or FIB-4 Score). A p value of <0.05 will be significant. Intention to treat analysis will be performed. Analyses will be conducted using SAS version 9.4. Multivariable regression models will be constructed.

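### Section 8.3 calls every p<0.05 significant, with no multiplicity control and no exploratory label for the secondary outcomes

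*Combined protocol and SAP*

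**What the plan says.** Section 8.3 (Statistical methods) gives a single significance rule, without distinguishing primary from secondary analyses: "A p value of <0.05 will be significant". Section 10.7 repeats the threshold for the comparison of serious adverse events.

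Section 1.3 lists six secondary outcomes:

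- Outcome 1 is "1) Change in PAI-1 after 16-week exercise regimen". This is the variable that sections 1.2 and 8.2 already make primary. The visit schedule has laboratory tests only at day 0 and week 20, so it is also the same measurement.
- Outcome 2 is the change in eight further markers: "von Willebrand Factor (vWF), P-selection, Protein S, Protein C, Factor VII, Factor VIII, Fibrinogen, Antithrombin".
- Outcome 3 is "Change in PAI-1 stratified by PNPLA3 genotype after 16-week exercise regimen". Section 1.1 names three genotypes: "rs738409 polymorphism (GG, GC and CC genotypes".
- Outcomes 4 and 5 are correlations of hemostatic markers with loss of hepatic fat and with VO2 max. The markers are not listed again.
- Outcome 6 is the change in health-related quality of life.

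For the laboratory outcomes, section 8.3 says "Student's t test and Mann-Whitney Rank Sum test will be used for secondary analysis of differences in numerical lab data". It gives no rule for choosing between the two tests, and it names no test for the correlations.

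The documents contain no multiplicity adjustment, no order of testing and no statement that secondary results are exploratory.

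**The concern.** A plan with one primary endpoint and many unadjusted secondary ones is acceptable if it says how the secondary p values are to be read. This plan does say, and what it says is that each one below 0.05 is significant.

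The trial asks whether exercise lowers clot risk in NASH, and section 2.1 describes disturbances in all three phases of hemostasis. If PAI-1 shows no difference but one of the eight markers, or one of the correlations, falls below 0.05, the plan's own wording allows that result to be reported as a significant effect on hemostasis. With 42 subjects enrolled and 15-20% attrition expected, such a result would be fragile.

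**Working it through.** The documents state no familywise error rate and no number of secondary tests, so there is no figure of the plan's own to reproduce here.

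**Inputs.**
- Per-test level 0.05 (section 8.3).
- Eight markers, three genotypes, two sets of correlations and at least one quality-of-life score (sections 1.1 and 1.3).
- Enrolment 28 + 14 = 42, of which six cover attrition (section 8.2). That leaves 36 evaluable, or 24 + 12 at 2:1.
- Correlation between markers: not in the documents. It is an assumption, varied from 0 to 0.9.

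**Count of tests.**

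| Outcome | Low count | High count |
|---|---|---|
| 1. PAI-1 (repeats the primary) | 0 | 1 |
| 2. Eight markers | 8 | 8 |
| 3. PAI-1 by genotype | 1 (interaction) | 3 (one per genotype) |
| 4. Hepatic fat correlations | 8 | 9 (with PAI-1) |
| 5. VO2 max correlations | 8 | 9 (with PAI-1) |
| 6. Quality of life | 1 | 1 |
| Total | 26 | 31 |

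Outcome 1 carries no separate chance of error if it is the same comparison as the primary. Leaving it out of the high count gives 30.

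**Independent tests, all nulls true.** P(at least one p<0.05) = 1 − 0.95^k.
- k = 8 (markers): 33.7%
- k = 9 (markers and quality of life): 37.0%
- k = 13: 48.7%; k = 14: 51.2%
- k = 26: 73.6%; k = 30: 78.5%; k = 31: 79.6%

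The expected number of false positives is 0.05k, whatever the correlation: 0.4 for the 8 markers and 1.5 for 30 tests.

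**Correlated markers.** Simulation under the global null with 24 + 12 subjects and the same correlation between every pair of markers. Hepatic fat, VO2 max and quality of life were generated independently, and the three genotype strata were of equal size.

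| Marker correlation | 9 between-arm tests | 26 tests | 30 tests |
|---|---|---|---|
| 0 | 37% | 73% | 78% |
| 0.3 | 34% | 69% | 74% |
| 0.5 | 29% | 63% | 68% |
| 0.7 | 23% | 52% | 57% |
| 0.9 | 16% | 38% | 43% |

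For the eight markers alone the simulated chance is 25 to 26% at correlation 0.5 and about 20% at 0.7.

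**Two candidate tests per marker.** Simulated at 28 v 14 with no true difference:
- Normal data: t alone 5.0%, Mann-Whitney alone 4.9%, either one 6.0%.
- Lognormal data: 4.0%, 4.8% and 6.8% (6.6% for either at 24 v 12, so about 6.7%).

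Over 30 tests, taking the smaller p value moves the familywise figure from 78.2% to 79.8% at correlation 0, and from 67.5% to 69.4% at 0.5. The number of endpoints drives the result; the second test hardly matters.

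**Cost of Holm across eight markers.** The first step is at 0.05/8 = 0.00625. With 28 + 14 − 2 = 40 degrees of freedom, 80% power at 0.05 corresponds to a noncentrality of 2.87. The same effect has about 50% power at 0.00625.

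**The case against.** The strongest reply is that the large percentages depend on choices the plan does not make. Sixteen to eighteen of the tests are marker-by-marker correlations, for which section 8.3 names no test. Stratifying by genotype need not mean three tests. The comparisons most clearly implied between arms are the eight markers and quality of life, which give 37% at most. The calculation also takes every secondary null as true, whereas section 2.1 argues that exercise helps all three phases of hemostasis. The trial has a single primary endpoint with its own two-sided alpha of 0.05, and section 1.1 presents it as the start of a programme of work.

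All of this stands as a limit on size. It also rules out three stronger readings that a reader might infer:

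- **That a false positive secondary result is more likely than not.** This needs the secondary nulls to be true (at least 14 of them if independent), the correlations to be counted, and marker correlation well below 0.9. The documents establish none of these.
- **That both tests are run on each marker and the better p value taken.** The sentence names two tests for a class of data, just as section 8.3 names chi-squared and Fisher's exact test together for categorical endpoints. It is fair to say only that no selection rule is given.
- **That the primary conclusion is compromised, or that the plan lets a secondary result rescue a null PAI-1 result.** The primary alpha is untouched, and no section provides for such a rescue.

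None of this supplies what is missing. An exploratory label would answer the concern, but the plan does not carry one.

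**Conclusion.** The concern holds as a defect in how secondary results may be claimed. With all secondary nulls true, the plan's rule yields at least one false significant result with these chances:

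- 34% for the eight markers if independent, about 25% at correlation 0.5 and about 20% at 0.7;
- 37% with quality of life added, if independent;
- 74% to 80% for 26 to 31 independent tests. For 30 tests this falls to about 57% at marker correlation 0.7 and 43% at 0.9.

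The test count is ours and the correlations are assumed. Even the narrowest of these families is well above the nominal 5%. The absent rule for choosing between Student's t and Mann-Whitney is a minor contributor, raising the per-marker error to about 6.0% (normal data) or 6.7% (lognormal data) if the smaller p value were taken. The primary PAI-1 inference is unaffected. The point should be corrected before analysis, but it does not threaten the trial's main result.

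**What to change.** In section 8.3:

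1. Reserve p<0.05 as 'significant' for the single primary PAI-1 comparison.
2. Report secondary outcomes 2 to 6 as exploratory: estimates with 95% confidence intervals and p values stated to be unadjusted.
3. Name one prespecified test per marker.
4. If a significance claim is wanted for the eight markers of outcome 2, apply Holm across them.

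Outcome 1 can be cross-referenced to the primary for clarity; removing it would not by itself control error.

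The change is to wording only and needs no new data or subjects. The price is that a nominal p<0.05 on a secondary outcome can no longer be claimed as significant. Under Holm, a marker with 80% power at 0.05 has about 50% at the first step. The documents give no power calculation for any secondary outcome, so no stated power target is lost.

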9.0 Confidentiality, Privacy and Data Management

See the Research Data Plan Review Form

10.0 Data and Safety Monitoring Plan

10.1 Periodic evaluation of data
[name] (hepatology) will serve as the independent medical monitor for the proposed research project and will meet with [name] bi-annually. Under the mentorship of [name], [name] will provide oversight for the conduct of the study and collectively we will follow the protocol proposed and ensure all eligibility criteria and consent requirements are met prior to enrolling a subject. All study

procedures and adverse event (AE) reporting will occur in accordance with the Penn State College of Medicine IRB approved protocol. These monitoring activities will remain in place until all participants have completed the intervention. [name] will review AEs on a rolling basis and quarterly. He will review study enrollment and any early termination of a subject's participation. Any issues requiring study modification or a change in the risk/benefit to a subject will be reported immediately to the IRB. A summary of AEs, study progress and protocol modifications will be sent to the IRB for review in the annual continuing review report.

10.2 Data that are reviewed

Safety data will be reviewed as will untoward events.

10.3 Method of collection of safety information

Case report forms will be utilized for AEs. Study visits will assess for AEs.

10.4 Frequency of data collection

[name] will review AEs on a rolling basis and quarterly. He will review study enrollment and any early termination of a subject's participation.

10.5 Individuals reviewing the data

[name] and [name]

10.6 Frequency of review of cumulative data

Quarterly

10.7 Statistical tests

Subjects will be compared in their randomized groups according to SAE occurrence. Chi-squared and Fisher's exact test will be used to analyze our categorical endpoints. A p value of <0.05 will be significant. Intention to treat analysis will be performed. Analyses will be conducted using SAS version 9.4.

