Whole blood will be drawn in the Penn State Hershey GCRC (hours 730a-4p) by trained GCRC nursing or NASHFit research staff. Whole blood will be obtained and placed into the following tubes in the amounts described below [total nine teaspoons (tsp) of blood]:

- Three 3mL lavender (EDTA) top tubes (1.8 tsp)
- Two 4.5mL green (sodium heparin) top tubes (1.8 tsp)
- Three 6mL red top tube (3.6 tsp)
- Three 2.7mL blue (sodium citrate) top tubes (1.6 tsp)

Samples will then be delivered by NashFit study personnel to both the Clinical Laboratory for processing to serum and platelet poor plasma and also to [name] in the Institute for Personalized Medicine (IPM) for processing prior to transfer to the Endocrine Core Laboratory. Samples will be frozen and picked up from the Clinical Laboratories by IPM staff and brought to the IPM for storage and also the Genome Sciences and Bioinformatics Core for Taqman assay performance. Coded samples will be shipped through the IPM to [name], Associate Professor in University Park for metabolomics analysis. Results will be sent back to the IPM per standard IPM operating procedure. Stool samples will be obtained from the subject at home with a home collection kit and mailed directly from the subject to [name] (collaborator), Assistant Professor of Medicine, Juniata College. Stool samples will be processed, analyzed with 16S rRNA testing and stored in [name] laboratory.

Intervention Conditions: The aerobic exercise protocol is adapted from the landmark NASH-exercise trials by Sullivan *et al*(91) and Bacchi *et al*(92) that demonstrated the efficacy of exercise in improving intrahepatic fat and body composition but did not evaluate the effect on hemostasis and thrombosis risk. Once subjects have passed screening, they will be randomized 2:1 into either the exercise or control group respectively (two exercise subjects per one control subject) using a computer-generated randomized scheme in blocks of six by an independent statistician ([name] Public Health Sciences).

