8.2 Sample size determination
Subjects will be randomized into two treatment groups. This is an efficient study design with increased power and is appropriate for the proposed exercise intervention. The primary outcome will be change in PAI-1 following a 16-week exercise course. Secondary outcomes are described above. Baseline levels of PAI-1 are between 35-45 ng/mL.(72, 74-76) Estimates for change in PAI-1 following exercise regimens of between 3-8 months duration range between 23-37% with >30% reduction only reported in regimens >6 months long.(72, 74-76) De Gues *et al.*(75) found an initial 24.5% reduction as measured at four months in PAI-1 levels in thirty healthy adults aerobically exercising 2.5 hours per week. We expect the exercise intervention to result in a 23% reduction (9 ng/dL) in PAI-1. We expect no change in PAI-1 levels in the control arm. We conservatively determined power calculations utilizing the standard deviations in the literature (2.0 for no exercise group and 14.0 for the aerobic exercise group). We expect a 15-20% attrition rate;(94) to account for this we will enroll an additional six subjects.

Based on these assumptions and a 2:1 enrollment ratio with two subjects in the aerobic exercise arm to every one subject in the standard of care arm, a total study enrollment size of 28 subjects in the aerobic exercise arm and 14 in the standard of care arm will achieve 80.74% power to detect a difference in mean PAI-1 at sixteen weeks of at least 9 ng/mL, using a two-sided, two-sample unequal variance t-test with a significance level (alpha) of 0.05. A total study enrollment of **42 subjects** is planned.

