11.0 Risks

This study is designed to assess the efficacy of exercise in patients with NASH. The main risks of any exercise protocol include physical injury (e.g. musculoskeletal), or an adverse cardiovascular event (myocardial infarction). All exercise sessions will be monitored by ACSM certified fitness professionals and an available physician will be available should any injury or cardiovascular event occur. In addition, there are several other risks related to the measures of secondary outcomes:

MRI scan:

- Discomfort related to claustrophobia from being inside an enclosed space for the MRI scan and loud banging noise during the study for which temporary hearing loss has been reported (wearing earplugs can help prevent this).

DXA scan:

- Radiation exposure from the DXA scan that is being used to determine body composition

Venipuncture (blood draw):

- Discomfort associated with removing blood by venipuncture (by needle from a vein) including mild discomfort and/or a black and blue mark at the site of puncture.
- Less common risks of venipuncture include a small blood clot, infection or bleeding at the puncture site, and on rare occasions fainting during the procedure.

Cardiopulmonary Testing:

- Maximal oxygen uptake testing involves exercising to exhaustion. Side effects may include, fainting, chest pains, weakness, vomiting, muscle soreness and headache.
- Risk of falling due to increasing speed and incline of the treadmill during exhaustive exercise.

Liver biopsy:(95)

- 5-20% musculoskeletal pain despite topical and deep anesthetic
- <1% risk of
 - Major bleeding
 - Infection
 - <Inadvertent organ puncture (e.g. kidney, lung, gallbladder, colon)

There is also an inherent risk in randomization as subjects are assigned to a study group by chance. The study program a subject is assigned to may prove to be less effective or have more side effects than the other study groups.

Incidental findings discovered through history & physical exam, pregnancy testing, blood draws, cardiopulmonary testing, imaging (MRI and DXA) and during the exercise protocol will be handled on an individual basis according to standard medical practice at the discretion of the study PI. These results will be communicated to not only the subject but also the subject's primary care physician and/or the appropriate medical specialist best suited for further evaluation.

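### The one planned between-arm safety comparison covers SAEs only and rests on p<0.05, which at 28 versus 14 subjects says little about safety; section 10.7 should report all AEs by arm with exact intervals

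*Combined protocol and SAP*

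**What the plan says.** Section 10.7 sets out the comparison of the arms on safety: "Subjects will be compared in their randomized groups according to SAE occurrence". The method follows: "Chi-squared and Fisher's exact test will be used to analyze our categorical endpoints", "A p value of <0.05 will be significant" and "Intention to treat analysis will be performed". It gives no rule for choosing between the two tests and does not say whether they are one- or two-sided. Section 8.3 adds no comparison of adverse events or injuries.

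Section 11.0 describes the hazard of the intervention: "The main risks of any exercise protocol include physical injury (e.g. musculoskeletal), or an adverse cardiovascular event". Section 10.3 shows that the data will exist: "Case report forms will be utilized for AEs".

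Outside this comparison, sections 10.1 and 10.4 provide rolling and quarterly review of AEs. Section 10.8 puts enrolment on hold when the independent medical monitor judges SAEs to exceed expectation. Neither refers to a p value.

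**The concern.** The safety analysis is narrower than the stated risk. A strain or fall that does not meet the SAE criterion is recorded on a form but enters no planned comparison of the arms, although it belongs to the first-named risk of the exercise programme.

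The SAE comparison that remains is a significance test in 42 subjects split 2:1. If it is unlikely to reach p<0.05 even when exercise does cause SAEs, a non-significant result carries little information. The plan asks for no estimate or interval that would show a reader how much harm is still compatible with the data.

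**Working it through.** **Inputs.** Arms of 28 and 14 (section 8.2; section 7.2 has subjects "randomized 2:1 into either the exercise or control group respectively"). Intention to treat, so these are the denominators. Alpha 0.05, with chi-squared and Fisher both named (section 10.7). Two-sided testing is my assumption. The documents give no expected SAE or exercise-injury rate, so the true rates in step 3 are assumptions too.

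**Step 1. The plan's own figure.** No power or threshold is stated for safety. The only power figure is for PAI-1: "28 subjects in the aerobic exercise arm and 14 in the standard of care arm will achieve 80.74% power". A two-sided Welch t-test with difference 9, SDs 14 and 2 and alpha 0.05 gives 80.74% at 22 versus 11, which is roughly the enrolment after 20% attrition, and 89.66% at a literal 28 versus 14. That is a separate matter. The figure says nothing about the safety test.

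**Step 2. Smallest significant excess.**

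Fisher, given k events in total: P(all k in the exercise arm) = C(28,k)/C(42,k), plus every table that is no more probable.

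- k=7, 7/28 v 0/14: 0.04389 + (0.00013 + 0.00312 + 0.02805) = 0.0752. Not significant.
- k=8, 8/28 v 0/14: 0.02633 + (0.00003 + 0.00081 + 0.00962) = 0.0368. Significant.

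Uncorrected chi-squared = N(ad−bc)²/(product of the four margins):

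- 6/28 v 0/14: 42×84²/(28×14×6×36) = 3.5, p=0.0614.
- 7/28 v 0/14: 42×98²/(28×14×7×35) = 4.2, p=0.0404.

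| Control events | Two-sided Fisher | Uncorrected chi-squared |
|---|---|---|
| 0/14 | 8/28 (p=0.037) | 7/28 (p=0.040) |
| 1/14 | 11/28 (p=0.036) | 10/28 (p=0.047) |

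The two named tests disagree at 7/28 v 0/14. The expected control count there is 7×14/42 = 2.3, so Fisher is the usual choice. With a continuity correction, chi-squared would need 9/28 (p=0.046). At 22 versus 11 the Fisher threshold is still 8 (p=0.031).

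**Step 3. Power.** Sum over all outcomes of P(x | 28, p₁) × P(y | 14, p₀), counting those with p<0.05 and the higher rate in the exercise arm. With a control rate of 0% this reduces to P(X≥8) for Fisher or P(X≥7) for chi-squared, X being binomial(28, p₁).

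| Assumed true SAE rates, exercise v control | Fisher | Chi-squared |
|---|---|---|
| 10% v 0% | 0.5% | 1.8% |
| 15% v 0% | 4.9% | 11.5% |
| 20% v 5% | 9.4% | 17.1% |
| 20% v 0% | 18% | 32% |
| 30% v 0% | 64% | 78% |

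**Step 4. What zero events would show.** The exact two-sided 95% upper limit for 0/n is 1 − 0.025^(1/n): 12.3% for n=28 and 23.2% for n=14.

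**The case against.** The strongest reply is that the trial's protection against harm does not run through this test, and that is right. A reader might infer that harm cannot be flagged until eight exercisers have an SAE. The documents do not support that. AEs are reviewed on a rolling and quarterly basis (10.1, 10.4), unexpected and probably related harms go to the IRB (19.1), and the hold on enrolment is a judgement by the monitor (10.8). The threshold of 7 or 8 belongs to the final comparison alone.

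Other stronger readings also fail:

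- *That the plan will declare exercise safe if p>0.05.* No section says so, and safety is neither a primary nor a secondary endpoint.
- *That the test could never detect harm.* At 30% v 0% Fisher has 64% power.
- *That a known majority of exercise injuries is left out.* It is plausible that most are not serious, but the documents do not define SAE (section 3.3.1 speaks of a severe event) and give no injury rate.
- *That biopsy harms will count against exercise.* The arm allocation of the ten biopsies is unclear, and the biopsy text in section 7.2 is partly redacted.
- *That the 12-week call to exercisers creates unequal safety follow-up.* Section 7.2 describes a questionnaire and does not say that it collects AEs.

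One objection bears on the remedy. Exercisers are seen at five supervised sessions a week, controls through weekly calls and monthly visits. Non-serious events will therefore be noticed more often in the exercise arm, and SAEs are less open to this bias. That is a fair reason to keep the SAE comparison, but not to leave injuries out of the by-arm report.

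Low power for SAEs is also common to any trial of this size, and the remedy will not raise it. That favours reporting an estimate with its interval over a test.

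**Conclusion.** The point holds for the final between-arm comparison. It covers SAEs only, although AEs are collected generally and musculoskeletal injury is the first-named exercise risk. It needs 8/28 v 0/14 by two-sided Fisher, or 7/28 by uncorrected chi-squared. At modest assumed rates it would usually miss a real excess: Fisher power is 4.9% at 15% v 0% and 9.4% at 20% v 5%. A non-significant result, even with no SAE among 28 exercisers, would leave true rates up to 12.3% open.

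The thresholds rest on two-sided testing and full enrolment, the power figures also on SAE rates that I assumed. That injuries are left out follows from the text; how many are left out cannot be established from it. No endpoint or enrolment decision changes. This is a worthwhile, inexpensive improvement to the safety analysis.

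**What to change.** In section 10.7:

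1. Report all AEs and all SAEs by randomized arm, as subjects with at least one event, with separate lines for musculoskeletal injury, cardiovascular events, and test- or procedure-related events.
2. For each line give counts, the risk difference and an exact 95% confidence interval. Drop p<0.05 as the safety criterion and state that the absence of a significant difference is not evidence of safety.
3. Count events over a fixed calendar window from randomization, the same length in both arms (for instance the 20 weeks of section 7.3). A window ending at the final visit would not do: section 7.2 lets exercisers extend training by up to four weeks, which may move that visit. List later events separately.
4. List biopsy-related events separately, whichever arm they arise in. Section 11.0 gives 5-20% musculoskeletal pain after biopsy, so ten biopsies could add about 0.5 to 2 events (10×0.05 to 10×0.20) to the injury line.
5. State that non-serious AEs are observed more closely in the exercise arm, and keep the SAE line beside the all-AE line for that reason.

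The cost is wording and a few tables from data already collected, with no new visits or subjects. The intervals will be wide, and the all-AE comparison can be read only with the caveat in item 5.
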